## Research Proposal

### 1 INTRODUCTION AND BACKGROUND

With an estimated 19.3 million new cancer cases worldwide in 2020, breast cancer in women overtook lung cancer as the most common cancer for the first time. Surgery is the most commonly used treatment for Breast Cancer, but it can lead to some complications, such as wound bleeding, infection, subcutaneous effusion, flap necrosis, limb dysfunction and Breast cancer-related Lymphedema (BCRL). Among them, BCRL can lead to upper limb dysfunction, muscle weakness, appearance impairment, anxiety and depression and other physical and psychological problems in breast cancer patients, which seriously affect the postoperative rehabilitation and quality of life of patients, and BCRL is difficult to cure once it occurs. According to relevant literature reports, the incidence of BCRL is about 21.4%, which is a widespread problem.

BCRL is due to a variety of breast cancer treatment methods damage the lymphatic system, resulting in lymphatic vessel fracture and morphological changes in the affected limb, so that the lymphatic fluid can not smoothly return, so that the affected arm of patients with swelling and pain, severe cases will cause infection and tissue fibrosis. At present, physical treatment, drug treatment or surgery can improve edema symptoms in different degrees, but due to the longer course of treatment, high cost, difficult lasting effect and other problems, so that many patients can not adhere to the treatment. BCRL has been recognized as a difficult point in the rehabilitation of patients, and medical workers need to pay attention to it.

Due to the lack of understanding of lymphedema in most patients, the initial manifestations of BCRL are easy to be ignored by patients, resulting in difficulties in the early prevention and detection of edema. Some domestic studies investigated local patients with the knowledge of lymphedema prevention after breast cancer surgery, and the results showed that the patients had a poor grasp of relevant knowledge, with an average score rate of 25.18%, which was significantly lower than the international median awareness rate of lymphedema. Since BCRL is difficult to cure once it occurs, researchers pay more and more attention to the prevention and early intervention of lymphedema, and improve the awareness and education of patients about the risk of lymphedema, which has become a necessary measure to improve the quality of life of breast cancer patients.

At present, knowledge, attitude and practice theory is widely used in rehabilitation guidance and education of patients. Based on KAP theory and combined with the best evidence of upper limb lymphedema prevention in patients after breast cancer surgery, this study plans to formulate a prevention plan for upper limb lymphedema in patients after breast cancer surgery, and apply this plan in clinical practice, so as to improve patients' cognition of lymphedema and promote patients to master and take positive rehabilitation behaviors. So as to reduce the incidence of upper limb lymphedema, improve the grip strength and function of the affected upper limb, and improve the quality of life of patients.

### 2 METHODS

#### 2.1 Design

This study was a randomized controlled experimental study. The study population included breast cancer patients who received advanced chemotherapy in a Class iii Grade

A public hospital in Xi 'an, Shaanxi Province, China from March 2020 to November 2020.

## 2.2 Sample

Inclusion criteria: (1) Female patients were  $\geq 18$  years old; (2) Pathological puncture confirmed breast cancer with unilateral, no recurrence, and no metastasis; (3) Patients with clinical TNM stage I ~III; (4) Patients with proposed surgery and 6 or more chemotherapy; (5) The patient was conscious and aware of his condition, with no cognitive impairment or communication problems. Exclusion criteria: (1) Patients who had cancer other than breast cancer; (2) Patients who had history of arm or neck trauma, infection or surgery; (3) Patients who had serious diseases such as cardiovascular, cerebrovascular, liver, kidney, etc; (4) Patients who had upper limb disability or the affected limb has edema before surgery; (5) Patients who had thrombus in the blood vessels of the affected limb.

## 2.3 Power analysis

This study used PASS 15.0 to calculate the sample size, using two-sided test,  $\alpha = 0.05$  and  $1 - \beta = 0.8$ . According to the literature,  $P_1$  was taken as 30% and  $P_2 = 5\%$ . The final calculation yielded  $N_1 = N_2 = 44$ , considering the 20% loss to follow-up rate after surgery, and the final total sample size was set at 106 cases, with 53 cases in the intervention group and 53 cases in the control group.

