#### 3.2.1 Assessment of upper limb edema on the affected side:

using an inelastic flexible ruler, the circumference of the wrist was measured at five locations: flat wrist stripes, 10cm, 20cm, 30cm and 40cm above the wrist stripes. The upper limb could be divided into four truncated cones, and the measurement value was accurate to 0.1cm. The upper arm volume can be obtained by using the formula, where  $\pi = 3.14$ , each h is 10 cm, C1 and C2 are the circumference of the two measuring points immediately adjacent to each other, and then the upper arm volume is obtained by adding up the limb volumes at several locations. According to the International Society of Lymphatics, a volume difference of 10% or more is defined as lymphedema, less than 20% as mild lymphedema, 20% to 40% as moderate lymphedema, and more than 40% as severe lymphedema.

Secondary outcome measures:

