#### 4 Data analysis

SPSS21.0 software was used, a two-sided test was set, and  $\alpha$  was set at 0.05. The normality of measurement data was expressed as mean  $\pm$  standard deviation ( $\pm s$ ), and two independent sample t-test was used. When not normal, the median and interquartile range [M(Q)] were expressed using the Mann-Whitney U test. Enumeration data were expressed as frequency and constituent ratio using 2 test. Mann-whitney U test was used for grade data.

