#### 5 RESULTS

In this study, a total of 108 patients completed the baseline survey (T0), 56 in the control group and 52 in the intervention group. A total of 11 patients fell off during the study (6 in the control group and 5 in the intervention group), and a total of 97 patients completed the study (50 in the control group and 47 in the intervention group), as shown in Figure 1.

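### Does planning on a 30% lymphedema rate, when the background section cites about 21.4%, undermine the stated 80% power?

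*Protocol*

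**What the plan says.** Section 2.3 (Power analysis) uses a two-sided test with α = 0.05 and 1 − β = 0.8. It cites the literature for its rates: P1 "was taken as 30% and" P2 is set at 5%. The result is 44 per arm, raised to 53 per arm (106 in total) after "considering the 20% loss to follow-up rate after surgery".

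Section 1 (Introduction and background) gives a different figure: "According to relevant literature reports, the incidence of BCRL is about 21.4" per cent. It names no population, diagnostic threshold or length of follow-up for it.

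Three other sections bear on which rate is plausible and how it is tested. Section 2.2 restricts entry to "Patients with proposed surgery and 6 or more chemotherapy". Section 3.2.1 sets the endpoint: "a volume difference of 10% or more is defined as lymphedema". Section 4 assigns a chi-square test to count data (the symbol is lost in the extracted text) and mentions no continuity correction.

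Section 5 reports 108 patients at baseline and 97 completers, 50 control and 47 intervention.

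**The concern.** Two incidences for the same condition, both credited to the literature, stand in one short protocol. The sample size rests on the higher one, which is the one that gives the smaller trial, and no reason is given. A reader could suspect that 30% was picked to make the sample feasible.

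If the true control rate were near 21.4%, the trial would have well under 80% power for its primary outcome. A non-significant result might then be taken as evidence that the prevention programme does not work, when the trial was simply too small to show it.

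**Working it through.** **Inputs.** P1 = 0.30, P2 = 0.05, two-sided α = 0.05, power 0.80, 44 evaluable or 53 enrolled per arm (section 2.3); alternative P1 = 0.214 (section 1); 50 and 47 completers (section 5). The protocol does not label P1 and P2 by arm. I take P1 as control, which fits the aim of prevention.

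**Step 1: reproduce the 44.** With p̄ = (P1 + P2)/2 and d = P1 − P2,

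n = [1.96·√(2p̄(1−p̄)) + 0.842·√(P1(1−P1) + P2(1−P2))]² / d².

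For 0.30 vs 0.05, p̄ = 0.175 and d = 0.25, so n = 35.1, rounded up to 36. The continuity-corrected size is (n/4)·[1 + √(1 + 4/(n·d))]². Using the unrounded 35.06 it gives 42.7, rounded up to 43. That is within one patient of the stated 44, so section 2.3 is consistent with a two-sided, continuity-corrected calculation at its own inputs.

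**Step 2: power at 44 per arm.** Let se0 = √(2p̄(1−p̄)/44) and se1 = √[(P1(1−P1) + P2(1−P2))/44]. Power is Φ[(d − c − 1.96·se0)/se1], with c = 0 uncorrected or c = 1/44 = 0.0227 corrected.

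- 0.30 vs 0.05: se0 = 0.0810, se1 = 0.0765. Uncorrected Φ(1.19) = 88.3%; corrected Φ(0.895) = 81.5%.
- 0.214 vs 0.05: se0 = 0.0722, se1 = 0.0700. Uncorrected Φ(0.32) = 62.6%; corrected Φ(−0.002) = 49.9%.
- 0.214 vs 0.0357 (sixfold ratio kept, 0.214 × 5/30): se0 = 0.0705, se1 = 0.0679. Uncorrected Φ(0.59) = 72.3%; corrected Φ(0.26) = 60.2%.

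**Step 3: all methods and sample sizes.** The exact column enumerates both binomials under the uncorrected chi-square test.

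| Evaluable n | Rates | Corrected | Uncorrected | Exact chi-square |
|---|---|---|---|---|
| 44 / 44 | 30% vs 5% | 81.5% | 88.3% | 91.8% |
| 44 / 44 | 21.4% vs 5% | 49.9% | 62.6% | 67.6% |
| 44 / 44 | 21.4% vs 3.6% | 60.2% | 72.3% | 78.8% |
| 50 / 47 | 30% vs 5% | 85.6% | 91.1% | 93.6% |
| 50 / 47 | 21.4% vs 5% | 54.5% | 66.5% | 70.0% |
| 50 / 47 | 21.4% vs 3.6% | 65.1% | 76.1% | 80.5% |
| 53 / 53 | 30% vs 5% | 89.3% | 93.5% | 95.3% |
| 53 / 53 | 21.4% vs 5% | 60.1% | 70.9% | 73.6% |
| 53 / 53 | 21.4% vs 3.6% | 70.7% | 80.2% | 84.2% |

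**Step 4: how near 30% must P1 be?** With 44 per arm and P2 = 5%, power stays at 80% or more down to P1 of about 29.5% (corrected), 26.5% (uncorrected) or 25% (exact chi-square, 80.4% at 25%).

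**Step 5: do the two figures describe the same quantity?** The 21.4% appears in a passage on how common the condition is. The 30% is a planning rate for patients selected for surgery plus six or more chemotherapy courses, judged by a 10% volume criterion and last assessed at the sixth course (section 3.1). The protocol contains nothing that makes these the same quantity.

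**The case for a change.** The strongest case for acting is that the sensitivity is real and the remedy cheap. With P2 held at 5%, no method and no sample size in the document reaches 80% at 21.4%. On the corrected formula, the one that comes closest to the stated 44, there is almost no margin below 30%. Some design features give no evident support for an above-background rate: stage I to III disease, exclusion of limbs already swollen before surgery, and a last assessment only five 21-day cycles, about 15 weeks, after the first course. One or two sentences in section 2.3 would let a reader judge a null result properly.

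The arithmetic in that case stands, and so does the observation that the protocol never explains its choice. What does not stand is the step to a defect. Section 2.3 prints the 80% together with P1, P2, α and N, so the figure is openly conditional. The steepest fall also comes from lowering P1 while fixing P2, which weakens the assumed effect as well as the baseline: the risk ratio goes from 0.05/0.30 = 0.17 to 0.05/0.214 = 0.23. With the ratio kept, the uncorrected chi-square has 79% to 84% power across the three sample sizes.

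A table of such powers in section 2.3 could also mislead. Every figure treats patients as independent, whereas section 2.4 allocates four medical groups, two per arm. With 22 evaluable patients per group and an assumed intracluster correlation of 0.01 to 0.05 (the protocol gives none), the design effect 1 + 21·ICC runs from 1.21 to 2.05. Corrected power at 30% vs 5% would then be about 72% down to 41%, before allowing for there being only four units. That is a separate matter, but it shows that a finely graded range over P1 alone would suggest more precision than the design supports.

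**Conclusion.** No change is needed. The stated 44 per arm reproduces to within one patient and gives 81% to 92% power, depending on the method, at the 30% vs 5% it was planned on. The protocol does not say why 30% suits this population, but 21.4% is a general incidence that neither contradicts nor displaces it. Deciding between them would need the cited literature, which is not available here.

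If 21.4% did apply, power at 44 per arm would be about 50% to 68% with P2 at 5%, or 60% to 79% with the sixfold ratio kept. These figures assume that P1 is the control rate and that patients are independent.

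Section 5 reports that follow-up is complete, so explaining the two rates now would change no enrolment, analysis or result. If the primary comparison is null, the confidence interval for the difference will show what the data can exclude better than a power range written afterwards. What remains is a missing explanation that an informed reader can allow for.

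### The planned 53 per group does not allow for the stated 20% loss: it leaves about 42 evaluable patients, not the required 44

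*Protocol*

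**What the plan says.** Section 2.3 (Power analysis) of the protocol sizes the trial with a two-sided test at α = 0.05, 80% power, and event proportions of 30% and 5%. It reports a result of 44 patients per group. It then makes an allowance for attrition: "considering the 20% loss to follow-up rate after surgery, and the final total sample size was set at 106 cases". The total is split equally, which gives 53 per arm. The protocol gives no formula for the step from 44 to 53.

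Section 5 (Results) gives the numbers reached: "a total of 108 patients completed the baseline survey (T0), 56 in the control group and 52 in the intervention group". It reports 11 patients lost, 6 in the control group and 5 in the intervention group, and 97 completers, 50 and 47 respectively.

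**The concern.** A loss-to-follow-up rate is a share of the patients enrolled. The enrolled number must therefore be large enough that, once that share is removed, the required evaluable number is left. That means dividing the evaluable number by one minus the loss rate. Multiplying it by one plus the loss rate always gives a smaller answer. The step from 44 to 53 looks like multiplication.

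At stake is whether the planned size does what the paragraph says it does. A reader is told that 106 patients protect the calculation against a 20% loss. If they do not, then the size, the loss rate and the evaluable target cannot all be right, and the power claim at the assumed loss rests on fewer patients than the calculation asked for.

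**Working it through.** **Inputs, all from section 2.3:** two-sided α = 0.05; power 0.80; proportions 0.30 and 0.05; 44 per group before attrition; loss 20%; 53 per group (106 in total) after attrition. From section 5: 108 at baseline (56 and 52), 11 lost, 50 and 47 completers.

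**1. The plan's 44.** With mean proportion (0.30 + 0.05)/2 = 0.175 and difference 0.25, the pooled normal formula without continuity correction is

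n = [1.96 × √(2 × 0.175 × 0.825) + 0.8416 × √(0.30 × 0.70 + 0.05 × 0.95)]² / 0.25² = (1.0532 + 0.4271)² / 0.0625 = 35.06, rounded up to 36.

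The continuity correction is n/4 × [1 + √(1 + 4/(n × 0.25))]². With n = 35.06 it gives 42.7, rounded up to 43. If 35.06 is first rounded up to 36, it gives 43.6, rounded up to 44. The stated 44 is therefore consistent with a continuity-corrected calculation, and I take it as given.

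**2. The plan's 53.**

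- Multiplying: 44 × (1 + 0.20) = 52.8, rounded up to 53; 2 × 53 = 106. This reproduces the printed figures exactly.
- Dividing: 44 / (1 − 0.20) = 55; 2 × 55 = 110. This does not.

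**3. What 53 per group delivers.**

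- Evaluable after 20% loss: 53 × 0.80 = 42.4 per group, a shortfall of 44 − 42.4 = 1.6.
- In total: 106 × 0.80 = 84.8, against the required 88.
- Largest loss that still leaves 44: 1 − 44/53 = 0.170, or 17.0%.
- Enrolment gap: 55 − 53 = 2 per group, 110 − 106 = 4 in total.

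**4. Cost in power.** Power at 30% versus 5%, two-sided 5%, with patients treated as independent. The first three rows enumerate all pairs of binomial outcomes.

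| Method | 44 per group | 42 per group |
|---|---|---|
| Chi-square with Yates correction, exact | 83.9% | 81.3% |
| Fisher's exact test, exact | 85.4% | 84.6% |
| Uncorrected chi-square, exact | 91.8% | 90.4% |
| Continuity-corrected normal formula, approximate | 81.5% | 79.2% |

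The loss is between 0.8 and 2.6 percentage points. Only the approximate formula goes below the 80% target, by less than one point.

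**5. What happened.** Observed loss was 11/108 = 10.2% overall (6/56 = 10.7% control, 5/52 = 9.6% intervention), below the 17.0% that 53 per group tolerates. Both groups finished above 44. With 50 and 47 patients, exact power at the planning rates is 88.7% (Yates), 91.0% (Fisher) and 93.6% (uncorrected chi-square).

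**The case against.** There are four fair points on the other side.

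- *The multiplication is inferred.* The protocol prints no formula, and adding a percentage to the required number is a common shorthand. If the 20% was meant as a surcharge on 44, then 53 follows. It is true that the mechanism is an inference. But the text calls the 20% a rate of loss to follow-up, and section 5 counts losses out of those who entered at baseline. The shortfall also does not depend on how 53 was reached: 20% lost from 53 leaves fewer than 44.
- *The power target is essentially kept.* At 42 per group every exact calculation exceeds 80%. This stands, and it limits the weight of the point. It does not make the sentence correct, because the paragraph sets 44 as the number required.
- *The shortfall never occurred.* Loss was about 10%, and 50 and 47 patients completed. This also stands, as a matter of consequence. A planning statement is judged on its own assumptions, and at 20% loss this one fails.
- *Other design features matter more.* Section 2.4 allocates four medical groups, two to each arm, while section 2.3 sizes the trial as if patients were individually randomised. Any clustering could well outweigh 1.6 patients per group. That is a separate question, and neither excuses nor enlarges this error.

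**Conclusion.** The concern holds. The sample size in section 2.3 is wrong on its own assumptions: 53 per group yields 42.4 evaluable patients at the stated 20% loss, 1.6 short of 44, and it covers a loss of 17.0%, not 20%. Enrolment consistent with the stated loss would have been 55 per group, 4 more patients in total.

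The practical effect is small, at most about 2.6 points of power, and the reported loss was low enough that the shortfall did not arise. The correction should be made because the figure is the trial's sample-size justification, not because the result is endangered.

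This conclusion takes 44 as the required number and reads the 20% as a share of patients enrolled. The power figures further assume the protocol's 30% and 5% and independent patients, with no allowance for clustering.

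**What to change.** In section 2.3, keep 53 per group (106 in total) as the planned size, and add a sentence, marked as a correction, saying that this number preserves 44 evaluable patients per group for losses of up to 17%, and that a 20% loss would have required 55 per group (110 in total). The label matters: silently replacing 20% with 17% would rewrite a planning assumption after the losses are known.

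Changing the target itself to 110 serves no purpose now, since section 5 reports recruitment and follow-up as finished, and it would present a planned size that was never the plan.

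The cost is one sentence, with no change to enrolment, data collection or analysis.

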## 2.4 Randomization

The unit admitting breast cancer was divided into four medical groups, whose members had been trained in homogeneous surgical operations. As each medical group managed fixed patients and wards, patients in different medical groups were treated in different wards. To avoid contamination between the intervention and control groups, the study was conducted in regional randomized groups based on departmental medical groups (block size is 4). Four labels were placed in four opaque envelopes, two with 0 and the other two with 1. Four physicians representing their respective groups drew the envelopes, and the patients enrolled in the two medical groups with "0" were designated as the control group, while the other two groups were designated as the intervention group.

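### Four medical groups were randomised, two per arm, but the sample size and tests treat patients as independent, so the stated 5% alpha and 80% power are not assured

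*Protocol*

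**What the plan says.** Section 2.4 divides the unit into "four medical groups, whose members had been trained in homogeneous surgical operations". Each manages its own patients, and "patients in different medical groups were treated in different wards". To avoid contamination, "the study was conducted in regional randomized groups based on departmental medical groups (block size is 4". The mechanism is a single draw: "Four labels were placed in four opaque envelopes, two with 0 and the other two with 1". One physician drew for each group. All patients of the two groups that drew 0 became controls, and all patients of the other two received the intervention. No patient-level randomisation is described.

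Section 2.3 gives the sample size: "This study used PASS 15.0 to calculate the sample size, using two-sided test", alpha 0.05, power 0.8, risks of 30% and 5%, 44 per arm. The only inflation is "considering the 20% loss to follow-up rate after surgery", which leads to 53 per arm and 106 in total. No ICC, design effect or number of clusters appears.

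Section 4 fixes the tests. For normal data, "two independent sample t-test was used". Non-normal and graded data get the Mann-Whitney U test. For counts, "Enumeration data were expressed as frequency and constituent ratio using 2 test" (the chi symbol is lost in the text as read). Section 2.1 calls the study a randomised controlled study and does not mention clusters. Section 5 reports 97 completers, 50 control and 47 intervention, without numbers per medical group.

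**The concern.** The unit of randomisation is the medical group, so four units were randomised. The block size of 4 in section 2.4 can only describe that one draw. Patients of one group share staff and ward. Section 3 also delivers the programme partly in shared form, through lectures, seminars, a chat group and mutual-help groups on the ward. Some correlation within groups is therefore plausible, and nothing in the protocol shows that it is absent.

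Two things are at stake. First, the 5% alpha and 80% power were derived for uncorrelated patients. With positive correlation, t-tests and an uncorrected chi-square reject a true null hypothesis too often. Second, each arm consists of two teams in their own wards, so a difference between arms cannot be well separated from a difference between teams or wards, whichever test is used.

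This is not a detail left to an unseen SAP. The protocol itself fixes the allocation, the sample-size inputs and the tests, and they do not fit together.

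**Working it through.** **1. The protocol's own figure.** Inputs from section 2.3: P1 = 0.30, P2 = 0.05, two-sided alpha 0.05, power 0.80. The mean risk is 0.175.

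- Uncorrected: n = [1.96·√(2·0.175·0.825) + 0.842·√(0.30·0.70 + 0.05·0.95)]² / 0.25² = 35.1, so 36 per arm.
- Continuity-corrected: (35.1/4)·[1 + √(1 + 4/(35.1·0.25))]² = 42.7, so 43 per arm, against 44 stated.
- Loss: 44·1.2 = 52.8, so 53 per arm.

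The stated size is thus that of an individually randomised two-proportion design, with nothing added for clustering.

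**2. Assumptions.** The documents give neither ICC nor group sizes. Assumed: ICC 0.01, 0.02 and 0.05, and four equal groups of m = 44/2 = 22 evaluable patients.

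**3. Effective size.** Design effect DE = 1 + (m − 1)·ICC = 1 + 21·ICC. Effective n per arm = 44/DE. With two groups per arm, effective n = 2m/[1 + (m − 1)·ICC], which cannot exceed 2/ICC however large m becomes. Setting it to 44 gives m = 44(1 − ICC)/(2 − 44·ICC).

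| ICC | DE | Effective n per arm | Ceiling 2/ICC | Group size for an effective 44 |
|---|---|---|---|---|
| 0.01 | 1.21 | 36.4 | 200 | 28 |
| 0.02 | 1.42 | 31.0 | 100 | 39 |
| 0.05 | 2.05 | 21.5 | 40 | none |

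**4. Type I error of the patient-level tests.** Chi-square: beta-binomial simulation, two groups of 22 per arm, 400,000 runs. t-test: normal data, 100,000 runs; the formula 2·[1 − Φ(1.96/√DE)] gives 0.050, 0.075, 0.100 and 0.171.

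| Test and common risk | ICC 0 | 0.01 | 0.02 | 0.05 |
|---|---|---|---|---|
| Chi-square uncorrected, 17.5% | 0.055 | 0.079 | 0.106 | 0.180 |
| Chi-square uncorrected, 30% | 0.053 | 0.078 | 0.107 | 0.181 |
| Chi-square uncorrected, 5% | 0.048 | 0.070 | 0.090 | 0.145 |
| Chi-square corrected, 17.5% | 0.023 | 0.038 | 0.055 | 0.111 |
| Chi-square corrected, 30% | 0.029 | 0.046 | 0.067 | 0.128 |
| Chi-square corrected, 5% | 0.005 | 0.012 | 0.019 | 0.048 |
| t-test | 0.050 | 0.075 | 0.100 | 0.176 |

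At 17.5% risk the corrected chi-square passes 5% between ICC 0.016 (0.0490) and 0.018 (0.0518). Unequal groups of 14 and 30 make matters slightly worse: at ICC 0.01, 0.02 and 0.05, 0.083, 0.113 and 0.196 uncorrected, and 0.040, 0.061 and 0.124 corrected. The achieved size, with an assumed split of 25 + 25 against 23 + 24, gives a similar picture: at ICC 0.05, 0.187 uncorrected and 0.129 corrected.

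**5. Power at 30% vs 5%, 44 per arm.** For independent patients the exact power is 0.918 uncorrected and 0.839 corrected. With clustering, the corrected patient-level test still rejects in 0.819, 0.803 and 0.768 of runs at ICC 0.01, 0.02 and 0.05, but at the type I errors in step 4.

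A group-level t-test uses one proportion per group and 4 − 2 = 2 degrees of freedom, with critical value 4.30 instead of 1.96. Its simulated power depends on how samples with zero within-arm variance (3-4% of runs) are counted:

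| ICC | Counted as rejections | Not counted |
|---|---|---|
| 0 | 0.464 | 0.426 |
| 0.01 | 0.416 | 0.381 |
| 0.02 | 0.379 | 0.347 |
| 0.05 | 0.309 | 0.281 |

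A noncentral-t approximation gives 0.436 at ICC 0 and 0.263 at ICC 0.05.

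**6. Randomisation test.** Four groups split 2:2 allow C(4,2) = 6 allocations. The smallest two-sided p-value is 2/6 = 0.33, so the draw alone cannot deliver significance at 5%.

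**The case against.** The strongest reply concerns the primary outcome. The stated 44 is close to the continuity-corrected formula (43) and well away from the uncorrected one (36), so the corrected chi-square is the test most consistent with section 2.3. That test is conservative at ICC 0. At 17.5% risk its type I error is about 4% at ICC 0.01 and 5.5% at 0.02, with about 80-82% power. At two of the three assumed ICCs the stated alpha and power therefore roughly hold. This stands as far as it goes. But section 4 does not say which chi-square is used, the t-tests on secondary outcomes have no such cushion, and at ICC 0.05 the corrected test errs in about 11% of cases.

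Second, the ICC may be small. All groups belong to one unit, surgical training was homogeneous (section 2.4), and data collectors were uniformly trained and unaware of grouping (section 3.1). These facts may lower the ICC but do not show it to be zero, and four groups cannot establish that.

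Third, the group-level test is itself weak. At a 5% risk its type I error is about 1-2% or 6%, depending on how zero-variance samples are treated. It can show how little four groups support, but it is no cure.

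Finally, avoiding contamination is a sound reason to allocate by group. The objection here is to the mismatch with sections 2.3 and 4, not to that choice.

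**Conclusion.** The concern holds and must be fixed. The protocol randomises four medical groups but sizes and tests the trial as if patients had been randomised individually. The claim is that alpha and power are not assured. How far they are off depends on an ICC that the documents do not give.

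For assumed ICCs of 0.01 to 0.05 and equal groups of 22, the true alpha at 17.5% risk is about 8-18% for an uncorrected chi-square and 4-11% for a corrected one; for the t-tests it is about 7.5-18%. A group-level test has roughly 43-46% power at ICC 0 and 28-31% at ICC 0.05 by simulation (26% by the noncentral-t approximation at ICC 0.05), so it falls well short of 80% at every ICC tried. If the ICC were exactly zero, the patient-level tests would keep about their nominal size or less. The confounding of arm with team and ward needs no assumed ICC to be a limitation.

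**What to change.** 1. **Sections 2.1 and 2.4:** describe the trial as cluster-randomised with two medical groups per arm, and give the number of patients in each group.
2. **Section 2.3:** state that 44 per arm and 80% power assume independent patients (ICC = 0, patient-level test) and are not the power of the four-group design. Add the 2-df power as a figure calculated after completion, with its assumptions: equal groups of 22, 30% vs 5%, roughly 43-46% at ICC 0 and 28-31% at ICC 0.05 by simulation, depending on how zero-variance samples are handled.
3. **Section 4:** report every outcome by medical group, with a group-level comparison (one summary per group, 2 df). Note that it rests on distributional assumptions and is poorly calibrated at low event rates. Label the patient-level tests as not adjusted for clustering, and say whether the chi-square is continuity-corrected.
4. **Status:** section 5 shows that the study is complete, so label the added analysis post hoc and the between-arm inference exploratory.

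The cost is wording in four sections and a small analysis. Each patient's medical group must be identifiable. The documents do not say that it was recorded, but allocation by group implies it. The price is wider intervals, a less favourable power statement and more cautious conclusions. None of this removes the limit set by two groups per arm.
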